### 6.4 STUDY INTERVENTION COMPLIANCE

At all times during cannabis consumption, a minimum of two members of the research team will be present to ensure compliance to the inhalation protocol. They will guide participants through the protocol and ensure that they comply with the protocol timing. If participants intentionally deviate from protocol (holding breath, taking secondary breaths) they will be instructed to refrain during future cycles. If deviation continues data will not be collected during that study visit, and the protocol will be stopped. Acceptable deviations may occur, such as participants coughing. In the instance of coughing, the protocol will be paused until the participant is ready to resume. While monitoring, researchers will evaluate when all cannabis has been exhausted. At this point the inhalation protocol will be ceased.

### 6.5 CONCOMITANT THERAPY

For this protocol, a prescription medication is defined as a medication that can be prescribed only by a properly authorized/licensed clinician. Medications to be reported are concomitant prescription medications, over-the-counter medications and supplements.

### 6.5.1 RESCUE MEDICINE

The study site will not supply rescue medication as dried cannabis flower is not being examined in the context of treatment of disease or symptom relief.

## 7 STUDY INTERVENTION DISCONTINUATION AND PARTICIPANT DISCONTINUATION/WITHDRAWAL

### 7.1 DISCONTINUATION OF STUDY INTERVENTION

If a participant experiences a cannabis-related severe adverse at any point during participation in the study, or new information regarding their health becomes available to them that would contraindicate cannabis use, they will be immediately discontinued from further trials. Investigators will inquire whether there have been any changes in health or prescription medication status each study visit. Severe cannabis related adverse events will be classified using the adverse event form, but will also by default include any instance of cannabis induced hyperemesis or any degree of psychosis. If a participant voluntarily withdraws, they will not be required to provide a reason, and no further data collection will occur. However, if a participant decides to withdraw following consumption of cannabis during a study visit, they will be required to remain in the laboratory for 4 hours following the moment of consumption, so that their safety may be monitored. Any adverse event that occurs will be recorded using an adverse event form.

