## 2.3 RISK/BENEFIT ASSESSMENT

### 2.3.1 KNOWN POTENTIAL RISKS

Largely owing to elicit status, a comprehensive risk profile of cannabis consumption has not been developed. There does, however, exist a number of immediate and long-range risks. It has been established that consumption of cannabis containing THC results in impairments in cognition and memory. In addition to these impairments, users may experience panic attacks. The most severe psychological risk of consuming cannabis is the development of a mild to severe psychotic episode, which occurs on rare occasions. The diverse effects of cannabis on the brain have resulted in the recommendation that cannabis should not be consumed prior to operating motor vehicles. Impairment may typically last between 3-4 hours, with some evidence indicating that in impairment can persist for 6-8 hours.

In addition to immediate psychological risks, cannabis consumption is associated with a number of physical risks. Smoking cannabis can result in a transient sinus tachycardia. Reports have associated cannabis use with acute cardiovascular events and stroke, although a causative relationship has not been established. Despite these physical risks, cannabis is largely considered safe. In rare instances, cannabis consumption can induce hyperemesis.

Cannabis use may also present immediate economic risks to some individuals. Due to the long-standing elicit status and the only recent legalization of recreational use, many employers still prohibit cannabis use by employees.

Long-range risks of cannabis use are less understood than acute risks. Physical and psychological risks have been identified, however, certain long-range risks have not been directly attributed to cannabis itself, due to the existence of certain behaviors or requisite activities associated with use. Physical long-range risks include reductions in pulmonary function, respiratory infection, and alterations in brain structure. Long-term cannabis use has been associated with an increased rate of development of schizophrenia, mood and

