Despite lacking a robust list of potential benefits of recreational use in healthy individuals, the justification for an investigation into the acute physiological effects of consumption is counter balanced by the rarity of acute adverse effects entirely attributable to cannabis use in these individuals. Cannabis induced hyperemesis and cannabis induced psychotic episodes are rare. While other more consequential risks of cannabis use such as acute coronary syndrome and stroke have been suggested, no investigation has identified a causal relationship. These reported acute cardiovascular risks are especially intriguing given the increasing popularity of use by athletes in and out of competition. Exercise is a potent transient cardiovascular stress, and many questions surrounding the effects of the combined stimulus of exercise and cannabis remain. Despite reports of acute risks of cannabis consumption, it should be noted that presently a much larger evidence-base suggests that recreational cannabis use is associated with long rather than short term health consequences.

Although the acute risks of cannabis use appear to be rare, current knowledge suggests that they may be inherent to use and therefore should be minimized, but cannot be completely avoided. An effective approach to ensuring participant safety in the context of cannabis use requires pre-eminent planning in the case of known acute risks, and selection of a population that does not possess an elevated risk of experiencing the most commonly reported adverse effects. The present study will monitor participants following cannabis consumption to ensure participant safety. Participants will be monitored until the effects of cannabis have subsided. Further, a dosage has been selected that is less potent and smaller than what is available for typical recreational use. Choice of dosage was selected as a dose that is likely to exert physiologically meaningful effects, but not impose elevated risk to participants. Participants in the present study will be experienced users, who will not be unfamiliar with the effects of consumption. Additionally, participants possessing commonly known risk factors that may predispose to acute risk will be excluded.

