Continuous blood pressure, heart rate, and electrocardiogram monitoring will occur prior to, and during cannabis administration (prior to exercise) on all visits where cannabis is consumed. This procedure will be followed throughout the entirety of the 40-minute cannabis consumption period. If either systolic or diastolic blood pressure exceeds 160mmHg or 90mmHg at rest, respectively, exercise will not be performed, and the study visit will not continue. If heart rate exceeds 100bpm or falls below 40bpm at rest, exercise will not be performed, and the study visit will not continue.

All research will be performed within the department of Human Health and Nutritional Sciences at the University of Guelph.

There are no planned interim analyses planned for the current trial.

A sub-group analysis will be performed, with participants divided by sex, to determine the existence of any sex differences in primary and secondary endpoints.

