### 7.2 PARTICIPANT DISCONTINUATION/WITHDRAWAL FROM THE STUDY

Participants are free to withdraw from participation in the study at any time upon request. This includes during the inhalation procedure.

If a participant wishes to withdraw during or after the inhalation of cannabis they will be required to remain in the laboratory for the requisite recovery period of 4 hours. Each hour subjective effects, heart rate, and blood pressure will be measured.

An investigator may discontinue or withdraw a participant from the study for the following reasons:

- Pregnancy
- If any severe adverse event (AE), or other medical condition or situation occurs such that continued participation in the study would not be in the best interest of the participant
- If the participant reports meeting an exclusion criterion (either newly developed or not previously recognized) that precludes further study participation
- Participant unable to complete study procedures

The reason for participant discontinuation or withdrawal from the study will be recorded. Participants who discontinue the study will be replaced to ensure that the required pre-determined statistical power is met.

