Throughout each smoking protocol, a member of the investigatory team will supervise participants to ensure maximal adherence. If the participant engages in behaviors that are likely to augment the cannabis dosage, such as prolonged breath holding, they will be instructed to cease such behaviors. This investigator supervision will ensure that participants are receiving the desired dose of cannabis.

After completion of study procedures, participants will be required to remain in the laboratory for a period of 4 hours beginning from the end of the cannabis inhalation procedure. This period of monitored recovery has been implemented in an effort to minimize the subjective effects of cannabis experienced by participants prior to their release from the laboratory. In addition, participants will be required to complete the drug effects questionnaire each hour following the completion of study procedures. This questionnaire will evaluate the extent to which participants are experiencing the subjective effects of cannabis. If participants indicate that they are still experiencing subjective effects at the end of the 4-hour recovery period via the DEQ, they will be required to remain until effects have subsided. Blood pressure and heart rate will also be monitored throughout the recovery period. Measurements will be taken each hour with the administration of the DEQ.

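### Protocol sections 2.3.3, 7.1, 7.2 and 8.2 contradict each other on post-inhalation recovery: withdrawers get a flat 4 hours, completers stay until reported effects have gone

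*Protocol*

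**What the plan says.** Four places in the Protocol deal with how long a dosed participant stays under observation. The SAP covers only the statistical section and is silent on this.

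- **2.3.3 (risk/benefit):** "Participants will be monitored until the effects of cannabis have subsided". No exception is made for anyone.
- **8.2 (after study procedures are completed):** participants are "required to remain in the laboratory for a period of 4 hours beginning from the end of the cannabis inhalation procedure". The DEQ, blood pressure and heart rate are taken hourly. If the DEQ still shows subjective effects at 4 hours, "they will be required to remain until effects have subsided".
- **7.1 (voluntary withdrawal after consuming):** "they will be required to remain in the laboratory for 4 hours following the moment of consumption". No extension is given. The section also says that data collection ends on voluntary withdrawal, but that any adverse event goes on the adverse event form.
- **7.2 (withdrawal during or after inhalation):** "they will be required to remain in the laboratory for the requisite recovery period of 4 hours". Subjective effects, heart rate and blood pressure are measured hourly. No clock start is given, and release does not depend on the readings.

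Three further provisions can end a visit on the staff's decision: resting heart rate or blood pressure outside limits (4.1), ECG abnormalities (8.2), and repeated departure from the inhalation procedure (6.4: "If deviation continues data will not be collected during that study visit, and the protocol will be stopped").

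**The concern.** As written, the release rule depends on how the visit ended. Two people with the same exposure and the same persisting effects would be handled differently: the completer is kept under 8.2, while the withdrawer may leave under 7.1 or 7.2. Staff who follow the withdrawal text exactly could breach the general promise in 2.3.3.

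What is at stake is supervision of people whom the study itself has dosed. A smaller data question follows. Section 9.3 places everyone who consumes cannabis in the safety analysis, yet the Protocol gives conflicting instructions on whether recovery readings are taken after a withdrawal.

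**Working it through.** No sample size, power or error rate is involved. The check compares the texts and does simple arithmetic on the Protocol's own durations.

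**Inputs**

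- Hold: 4 h (7.1, 7.2, 8.2).
- Consumption period, D: monitoring runs "throughout the entirety of the 40-minute cannabis consumption period" (4.1), so D is at most about 40 min.
- Duration of impairment (2.3.1): typically 3–4 h, with some evidence that "impairment can persist for 6-8 hours".

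**Step 1: clock start.** Measure from the first inhalation.

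- Completer (8.2): earliest release at D + 4 h, so up to 4 h 40 min.
- Withdrawer (7.1), if the clock starts when consumption starts: 4 h 00 min. Gap = D = up to 40 min.
- Withdrawer (7.1), if the clock starts when consumption ends: D + 4 h. Gap = 0.

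The gap is 0 to about 40 minutes. Someone who stops partway has inhaled for less than the full period, so the gap is smaller.

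**Step 2: missing extension.** Let E be how long effects reported on the DEQ last, counted from the same point as the 4 hours. A completer stays max(4, E) and a withdrawer stays 4, so the gap is max(0, E − 4).

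| E (h) | Gap (h) |
|---|---|
| 3 | 0 |
| 4 | 0 |
| 6 | 6 − 4 = 2 |
| 8 | 8 − 4 = 4 |

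Putting the 2.3.1 figures in for E is an assumption. That section speaks of impairment, whereas the trigger in 8.2 is self-reported subjective effects. Nor does 2.3.1 say from what point its hours are counted, so the gaps in steps 1 and 2 should not be added.

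**Step 3: who is covered.**

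| How the visit ends | Hold that applies by its wording | Stay until effects subside? |
|---|---|---|
| Procedures completed | 8.2 | Yes, by DEQ |
| Participant withdraws after inhaling | 7.1 and 7.2 | Not stated |
| Staff stop the visit after inhalation (4.1, 6.4, ECG in 8.2) | None stated | Only through 2.3.3 |

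The last group neither withdraws nor completes the procedures. Section 7.2 lists reasons for which an investigator may withdraw a participant, but attaches no hold to them.

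**Step 4: data collection.** Section 7.1 ends data collection on voluntary withdrawal, while 7.2 requires hourly measurements in the same situation. Section 6.4 stops data collection at a non-compliant visit without saying whether recovery readings are included. Adverse events are not in doubt: 7.1 and 8.3.4 both require them to be recorded.

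**The case against.** The best defence is that 7.2 already points to 8.2. Its wording presupposes a recovery period defined elsewhere, its hourly checks closely match those in 8.2, and the unqualified sentence in 2.3.3 can be read as covering everyone. This is a plausible account of the intention. It does not settle the text: 7.1 sets its own clock, 7.2 states a fixed duration, and neither carries the release condition. Staff should not have to infer it.

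Three other points stand and limit the finding.

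- Section 5.3 asks participants not to drive on the date of a cannabis visit and to arrange a trusted escort home. This lessens the consequence of early release, but does not reconcile the sections.
- A fixed hold after withdrawal may be deliberate, because participants may withdraw at any time and an open-ended stay raises a consent question. The documents do not say so, but the possibility means that a difference between withdrawers and completers is not in itself an error.
- For ECG abnormalities that need medical attention, 8.2 requires emergency services to be contacted at once, so that group is not left without provision.

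A reader might also infer that early stoppers are the strongest reactors and have the least protection. The documents do not establish this. The stop in 6.4 concerns intentional departure from the inhalation procedure, and no reason need be given for a voluntary withdrawal.

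**Conclusion.** The contradiction is real and should be corrected. The until-effects-subside condition appears in 2.3.3 and 8.2 but not in 7.1 or 7.2, and the clock start is worded differently in 7.1 and omitted in 7.2. The missing extension matters more than the clock, but only if subjective effects outlast 4 hours.

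Two stronger readings are tempting and not supported.

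- **That withdrawers would go home with 2–4 hours of impairment remaining while identical completers are kept.** This holds only if the 6–8 hour upper range applies and impairment shows as a positive DEQ. A completer who is impaired but reports no subjective effects may also leave at 4 hours.
- **That a visit stopped under 6.4 yields no safety data.** Adverse events are still documented and followed under 8.3.4, and the safety analysis in 9.4.4 is built on adverse events and names no analysis of hourly DEQ or vital signs. What is unclear is narrower: whether the hourly recovery readings are taken.

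The point concerns participant safety and consistency. No endpoint, power figure or efficacy analysis is affected.

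**What to change.** - Reconcile 2.3.3, 7.1, 7.2 and 8.2 so that the clock start and release condition are stated consistently and the sections refer to one another.
- State which recovery provision covers withdrawals, and which covers visits stopped by staff after inhalation under 4.1, 6.4 and 8.2.
- Clarify in 7.1 and 6.4 that the stop on data collection does not cover the hourly recovery readings described in 7.2.

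The clock start, the release condition, and whether either should differ after withdrawal are for the sponsor and IRB to decide. This review takes no position on them.

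The cost is a protocol amendment, a matching line in the consent form and, depending on what is decided, some extra supervised time. The statistical plan needs no change.

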### 7.2 PARTICIPANT DISCONTINUATION/WITHDRAWAL FROM THE STUDY

Participants are free to withdraw from participation in the study at any time upon request. This includes during the inhalation procedure.

If a participant wishes to withdraw during or after the inhalation of cannabis they will be required to remain in the laboratory for the requisite recovery period of 4 hours. Each hour subjective effects, heart rate, and blood pressure will be measured.

An investigator may discontinue or withdraw a participant from the study for the following reasons:

- Pregnancy
- If any severe adverse event (AE), or other medical condition or situation occurs such that continued participation in the study would not be in the best interest of the participant
- If the participant reports meeting an exclusion criterion (either newly developed or not previously recognized) that precludes further study participation
- Participant unable to complete study procedures

The reason for participant discontinuation or withdrawal from the study will be recorded. Participants who discontinue the study will be replaced to ensure that the required pre-determined statistical power is met.

### 7.3 LOST TO FOLLOW-UP

A participant will be considered withdrawn if he or she fails to return for a scheduled visit and is unable to be contacted by the study staff.

The following actions must be taken if a participant fails to return to the laboratory for a required study visit:

- The site will attempt to contact the participant and reschedule the missed visit within one day, and counsel the participant on the importance of maintaining the assigned visit schedule and ascertain if the participant wishes to and/or should continue in the study.
- Before a participant is deemed withdrawn, the investigator or designee will make an effort to regain contact with the participant. These contact attempts will be documented.
- Should the participant continue to be unreachable, he or she will be considered to have withdrawn from the study.

## 8 STUDY ASSESSMENTS AND PROCEDURES

### 8.1 EFFICACY ASSESSMENTS

Participants will be screened for eligibility using two separate screening procedures during the introductory visit. The first screening procedure will be an investigator generated eligibility questionnaire. This questionnaire will evaluate whether the participant fits inclusion criteria and does not meet any exclusion criteria. The second screening tool will be the PARQ+, a validated questionnaire designed to determine whether participants are fit to safely exercise. The PARQ+ may determine that a participant requires clearance from their physician. If they do not obtain a signed doctor's note, they will not be eligible to participate. All screening procedures will occur during the introductory visit, and within one week of the exercise control visit. Additionally, at the start of each study visit participants will be asked if there have been any changes to their health status, or prescription medication status.

Efficacy assessments of primary objectives are as follows:

- Arterial stiffness will be assessed before and after cannabis consumption with and without subsequent exercise under each condition, during each study visit. Carotid-femoral pulse wave velocity will be used to determine arterial stiffness. Carotid-femoral pulse wave velocity will be measured by placing a tonometer probe at the site of the carotid and femoral pulse. Pulse waveforms will be juxtaposed against a lead-II electrocardiogram to determine pulse wave velocity.
- Endothelial function will be characterized before and after cannabis consumption with and without exercise under each condition during each study visit. Endothelial function will be measured using brachial artery reactive hyperemic flow-mediated dilation. The brachial artery will be imaged using a General Electric Vivid-i ultrasound system. After 1 minute of imaging, a tourniquet placed on the antecubital fossa will be inflated to 220mmHg for a period of 5 minutes will imaging continues. After this period 3 minutes of ultrasound imaging will be recorded to assess the vasodilatory response to occlusion. The relative (%) change in arterial diameter following release of the tourniquet will be the primary endpoint.
- Muscle sympathetic nerve activity will only be performed before and after vaporizing of high THC cannabis. Microneurography will be performed by inserting a tungsten microelectrode into the peroneal nerve. Upon identification of a sympathetic nerve

bundle, baseline activity will be recorded for a maximum of 10 minutes. Participants will then follow the standard smoking protocol, while sympathetic activity is recorded during the rest period.

- Cardiac function will be assessed using echocardiography. Echocardiography will be performed prior to exercise during the exercise control visit, and will be performed after consumption of cannabis on each study visit. Ejection fraction, E/A ratio, myocardial twist, and myocardial strain have all been chosen as these are standard measures for evaluating respective aspects of cardiac function. The heart will be viewed via the parasternal and apical imaging windows, and will be imaged using the Vivid-I ultrasound system.

Efficacy assessments of secondary objectives are as follows:

- Blood pressure, heart rate, and myocardial oxygen demand will be determined using a Finapres device which measures beat-to-beat heart rate and blood pressure using a finger cuff. The product of these two endpoints will represent the rate-pressure product, an indicator of myocardial oxygen demand. These outcomes will be assessed in the 20-minute period following cannabis consumption during each study visit. Therefore, recordings will take place at rest and during exercise depending on the given study visit.
- Indirect calorimetry will be performed during all exercise bouts, and will be used to evaluate oxygen consumption and other cardio-respiratory measures such as respiratory exchange ratio, minute ventilation, and caloric expenditure. Participants will be instrumented prior to each exercise bout, and measurement will only take place during the exercise bout.
- Participants will also be asked to provide ratings of perceived exertion every 2 minutes during each exercise bout. Ratings will be collected using the 6-20 Borg scale of perceived exertion.
- Exercise performance will be quantified by numerous endpoints such as average power output, and total work completed in the allotted exercise period (20 minutes). These outcomes will be assessed using the manufacturer software provided with the cycle ergometer that will be used in all exercise bouts.

No results of primary or secondary endpoints will be shared with participants until the completion of the data collection period. If participants wish to see results from any of the primary or secondary endpoints, all results will be provided in aggregate.

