### 1.3 SCHEDULE OF ACTIVITIES (SOA)

Procedure	Introductory Visit (Visit 0), Day 0	Exercise Control Visit (Visit 1), Day 7±1 day	Phase I Cannabis Visit (Visit 2), Day 14±1 day	Phase I Cannabis + Exercise Visit (Visit 3), Day 21±1 day	Phase I Cannabis Visit (Visit 4), Day 28±1 day	Phase I Cannabis + Exercise Visit (Visit 5), Day 35±1 day	Phase II Cannabis Visit (Visit 6), Day 42±1 day	Phase II Cannabis + Exercise Visit (Visit 7), Day 49±1 day	Phase II Cannabis Visit (Visit 8), Day 56±1 day	Phase II Cannabis + Exercise Visit (Visit 9), Day 63±1 day
Informed Consent	X									
Eligibility Questionnaire	X									
Physical Activity Readiness Questionnaire	X									
Height	X									
Weight	X	X	X	X	X	X	X	X	X	X
Blood Pressure and Heart Rate	X	X	X	X	X	X	X	X	X	X
Urine Test	X	X	X	X	X	X	X	X	X	X
Inquiry of Changes to Health and Prescription Status		X	X	X	X	X	X	X	X	X
VO 2 Max Test	X									
Pulse Wave Velocity		X	X	X	X	X	X	X	X	X
Brachial Artery FMD		X	X	X	X	X	X	X	X	X
Echocardiography		X	X	X	X	X	X	X	X	X
20 Minute Maximal Cycling Exercise		X		X		X		X		X
Vaporization of High THC Cannabis			X	X				X	X	
Smoking of High THC Cannabis					X	X				
Vaporization of High CBD Cannabis							X			X
Indirect Calorimetry/CPET	X	X		X		X		X		X
Microneurography (MSNA)			X							
Stress Echocardiography			X		X		X		X	
Measurement of Continuous Blood Pressure		X	X	X	X	X	X	X	X	X
ECG	X	X	X	X	X	X	X	X	X	X
Impedance Cardiography		X		X		X		X		X
Drug Effects Questionnaire			X	X	X	X	X	X	X	X

*This study will use a randomized crossover design. Phase I of this study will occur prior to the initiation of phase II. If a participant enters the study in phase II, but did not participate in phase I, they will be required to complete the introductory and exercise control visits. Visits 2-5 and 6-9 will occur in a randomized order, which will be individualized for each participant.*

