## 5.5 STRATEGIES FOR RECRUITMENT AND RETENTION

We seek to recruit 20 individuals per phase, 10 of which will be female and 10 of which will be male. Participants will be recruited from the community in Guelph, Ontario. In line with our IRB approved methods, recruitment posters will be posted at the University of Guelph and around the city. A social media posting will be sent via Twitter from the official Human Performance and Health Research Laboratory account. Additionally, the study poster will be presented to students in undergraduate lectures at the University of Guelph. Participants may also be recruited by word of mouth. Each participant who completes a session of microneurography will be compensated \$100 CAD in line with typical institutional procedures.

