## 9.2 SAMPLE SIZE DETERMINATION

In accordance with our power calculation, 15 participants are required to have a power of at least 0.8 with an alpha of 0.05, for expected changes in measures of endothelial function (pilot work, change in FMD in response to exercise pre =  $4.8 \pm 2.5$  %, post =  $2.7 \pm 1.7$ %) (FMD in rats in response to cannabis smoke, pre =  $7.5 \pm 2.5$ %, post =  $2.4 \pm 1.4$  %), artery stiffness (pilot work, change in PWV pre =  $7.4 \pm 1.3$  m/s, post (at rest) =  $6.0 \pm 1.3$  m/s) and cardiac function (pilot work, peak longitudinal strain: pre =  $-18.3 \pm 1.2$  %, post =  $-17.0 \pm 1.9$  %), therefore we will recruit 20 participants in each phase of the study to account for potential dropout.

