## 9.3 POPULATIONS FOR ANALYSES

Only participants who complete all study procedures will be included for analysis of efficacy endpoints. All participants who consume cannabis at any time will be included in the analysis of safety endpoints.

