## 9.4 STATISTICAL ANALYSES

### 9.4.1 GENERAL APPROACH

Our study will be divided into two phases each of which will be analyzed independently. All tests of significance will be two-tailed, and statistical significance will be based upon an alpha error probability of 5% and a power for 80%. The data will be evaluated using both parametric and non-parametric tests, as applicable. If the data are found to be not normally distributed, the raw data will be transformed using an appropriate transformation model in order to perform the parametric assessments. Non-parametric tests will be performed on raw data. The data will be assessed as continuous and will be presented as means with standard deviations. A one-way analysis of covariance will be used to assess the treatment

effects (Phase I: exercise, vaporizing THC, smoking THC, vaporizing + exercise THC, smoking THC + Exercise, Phase II: exercise, vaporizing THC, vaporizing CBD, vaporizing + exercise THC, Vaporizing CBD + Exercise) on the primary endpoints. Covariates will be introduced into the models in order to assess the impact of certain potential factors on outcome, including fitness, blood pressure, resting heart rate, and any other factors that are observed during the study that appear to potentially influence the outcome.

Our secondary endpoints will be assessed using a repeated measures one-way ANOVA and paired t-tests. If there are significant interactions differences between pairs of means will be determined with a Bonferroni post-hoc test.

---

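### Read literally, the all-procedures rule lets a missed microneurography recording, scheduled only at the vaporised-THC rest visit, discard a Phase I participant's other efficacy data; the same visit's electrode insertion has no counterpart at the smoked-THC rest visit

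*Protocol*

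**What the plan says.** **Where the recording is made.** Protocol 8.1: "Muscle sympathetic nerve activity will only be performed before and after vaporizing of high THC cannabis". Section 4.1 confirms that it happens at one visit. The Schedule of Activities (1.3) marks it at Visit 2, the Phase I rest visit with vaporised high-THC cannabis. It is not marked at Visit 4, the smoked-THC rest visit, or at any Phase II visit. Section 8.1 describes an electrode placed in the peroneal nerve, a baseline recording, and further recording in the rest period.

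**Who is analysed.** Protocol 9.3, repeated in SAP section 3: "Only participants who complete all study procedures will be included for analysis of efficacy endpoints". Protocol 9.4.2, repeated in the SAP's primary-endpoint section, instead admits anyone who finishes at least one whole phase. It fills missing values with the mean of that participant's other measurements.

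**Numbers.** Protocol 9.2 says "15 participants are required to have a power of at least 0.8 with an alpha of 0.05", and "therefore we will recruit 20 participants in each phase of the study to account for potential dropout". The planning inputs are FMD, PWV and longitudinal strain; nerve activity is not among them. Section 7.2 allows withdrawal of someone who cannot get through the procedures, and replaces those who discontinue.

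**Payment.** Protocol 5.5: "Each participant who completes a session of microneurography will be compensated".

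**The concern.** Two separate problems come from the single recording.

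1. **Analysis population.** Microneurography is a listed procedure, and section 8.1 starts recording only once a sympathetic bundle has been found. It gives no rule for when none is found. Under the literal text of 9.3, an unsuccessful or refused recording costs the participant every efficacy endpoint, including those measured without difficulty. One technically demanding measure would then decide who counts for FMD, PWV and cardiac function in Phase I.

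2. **Rest contrast.** Phase I asks whether smoking and vaporising differ. At rest that means Visit 4 against Visit 2, and those visits differ by an electrode insertion as well as by inhalation method. Randomising visit order does not help, because the procedure is tied to the condition and not to calendar position. The hypotheses in 9.1 predict differences between the two methods (FMD and E/A ratio falling after smoked but not vaporised THC), so an effect of the procedure at Visit 2 could in principle mask or mimic them.

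**Working it through.** **Step 1. Reproduce the planned 15.** Inputs are the means and SDs in 9.2, alpha 0.05, power 0.80 and two-sided tests (9.4.1: "All tests of significance will be two-tailed"). The pre-post correlation r is not given; r = 0.5 is assumed. For a paired t-test (noncentral t), SD_diff = √(s₁² + s₂² − 2·r·s₁·s₂) and dz = difference / SD_diff.

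- Strain: √(1.44 + 3.61 − 2.28) = √2.77 = 1.664; dz = 1.3/1.664 = 0.781; n = 15 (power 0.803).
- FMD (exercise pilot): √(6.25 + 2.89 − 4.25) = √4.89 = 2.211; dz = 2.1/2.211 = 0.950; n = 11.
- PWV: √(1.69 + 1.69 − 1.69) = 1.3; dz = 1.4/1.3 = 1.077; n = 9.

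Strain reproduces the stated 15. The result depends on r:

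| r | Strain n | FMD n | PWV n |
|---|---|---|---|
| 0 | 26 | 19 | 16 |
| 0.3 | 20 | 14 | 12 |
| 0.5 | 15 | 11 | 9 |
| 0.7 | 11 | 8 | 7 |

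Recruiting 20 fits 15/(1 − 0.25) = 20, so five losses from all causes are tolerated.

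**Step 2. Apply 9.3 literally to Phase I, without replacement.** The documents give no success rate for the recording, so p is an assumed range. P(at least 15 of 20) = Σ C(20,k) pᵏ (1 − p)²⁰⁻ᵏ for k = 15 to 20. Power is for strain at r = 0.5.

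| Assumed success p | Expected n | P(n ≥ 15) | Power at expected n |
|---|---|---|---|
| 0.9 | 18 | 0.989 | 0.88 |
| 0.8 | 16 | 0.804 | 0.83 |
| 0.7 | 14 | 0.416 | 0.77 |
| 0.6 | 12 | 0.126 | 0.69 |

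With 10% other dropout as well (assumed), p = 0.8 retains 0.8 × 0.9 = 0.72, an expected 14.4, and P(n ≥ 15) = 0.495. At n = 14, power is 0.77 for strain but still 0.91 for FMD and 0.96 for PWV.

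**Step 3. Compare the two population rules.**

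- Under 9.3, a missed recording excludes the participant from all efficacy analyses.
- Under 9.4.2, someone without a recording who completes Phase II could stay in. A Phase I-only participant has not completed the whole phase, if the recording counts as part of it.
- The imputation clause implies that some missing values are expected. It cannot supply nerve activity after a failed session, because no other visit records it.
- Neither section says whether an attempted but failed recording counts as completed.

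**Step 4. The rest contrast.** Visits 2 and 4 carry the same rows in the Schedule of Activities apart from inhalation method and microneurography. No section gives a matching procedure at Visit 4, fixes the order of microneurography against the other measures, or adjusts for it. The exercise pair (Visits 3 and 5) and Phase II have no microneurography and are unaffected. The documents give no size or direction for an electrode effect. As illustration only, an assumed shift of 0.2 or 0.3 SD of the paired difference, with no true smoke-vapour difference, would raise the rejection rate at n = 20 from 5% to 14% or 25%.

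**The case against.** - **Replacement.** Section 7.2 replaces participants who discontinue, so the probabilities in step 2 hold only if nobody is replaced. This stands. A reader might infer that microneurography will take Phase I below 15; the documents do not support that. Replacement does not, however, remove selection on tolerating or succeeding at the recording. Nor is it automatic for someone who misses the recording but attends every visit, because withdrawal there is at the investigator's discretion.
- **The competing rule.** Section 9.4.2 and its imputation clause suggest that not every gap was meant to exclude a person. This also stands: exclusion is the literal reading of 9.3, not a settled outcome.
- **The threshold of 15.** At r = 0.5 only strain needs it. At 60% and 70% success, the chance of keeping 11 (FMD) is 76% and 95%, and of keeping 9 (PWV) 94% and 99%. The 13 to 99% range should not be read across to those endpoints.
- **The payment clause.** Paying those who complete a session does not show that some will not. It may mean that the recording is optional, but no section says so.
- **The rest contrast.** Recording at a single visit is a declared choice for an invasive measure. One might assume that leg immobilisation or a longer visit adds to the imbalance, but the documents mention neither. Nor do they show that the contrast is biased; they show only that two differences cannot be separated.

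**Conclusion.** The concern holds in two limited parts.

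1. As written, 9.3 and SAP section 3 would discard valid FMD, PWV and echocardiography data from a Phase I participant with no usable nerve recording. They also conflict with 9.4.2. For strain, without replacement and at r = 0.5, assumed success of 60, 70, 80 or 90% keeps at least 15 of 20 with probability 13, 42, 80 or 99%. With replacement, what remains is selection on recording success.

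2. The Phase I rest smoke-versus-vapour contrast is confounded with electrode insertion by design. Its size and direction are unknown, and it affects one of the two smoke-versus-vapour pairs.

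It may seem that taking Visit 2 baselines before inserting the electrode would remove the confounding. It would not: any insertion effect would then fall inside the Visit 2 pre-post change, with no match at Visit 4.

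**What to change.** 1. In Protocol 9.3 and SAP section 3, replace the all-procedures rule with evaluability defined per endpoint. State that absent or failed microneurography removes a participant from the nerve-activity analysis only. Reconcile this with 9.4.2 and its SAP counterpart, and say whether the recording is required or optional.
2. Pre-specify the exercise pair (Visits 3 and 5) as a sensitivity analysis of smoke versus vapour free of microneurography. It answers the question under exercise, so it supports the rest contrast but does not replace it.
3. Report the Visit 2/Visit 4 asymmetry as a limitation of the rest contrast.

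The cost is protocol and SAP wording and one further analysis of data already planned. No procedure or visit is added.
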